## 9.6 Safety Analysis

Patient listings will be provided for adverse experiences occurred from informed consent to exposure to the test article using Pre-Treatment Safety Analysis Set. Safety variables below will be analyzed using Treatment-Emergent Safety Analysis Set. For continuous variables, descriptive statistics (mean, standard deviation, N, median, min and max) will be provided for actual value and change from baseline at each visit. For categorical variables, N and percent will be provided for each category at each visit.

- Secondary Surgical Interventions related to the optical properties of the IOL
- Adverse Events (including secondary surgical interventions not-related to the optical properties of the IOL)
- Device Deficiencies
- Fundus visualization
- Intraocular Pressure
- Slit Lamp Examination
- Dilated Fundus Examination
- IOL Observations
- Subjective Posterior Capsule Opacification
- Posterior Capsulotomy
- Lens decentration and tilt
- [REDACTED]
- Laser Flare meter

- Subjective symptoms
- Problems during surgery

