#### (4) Eye Examinations Schedule

As shown in Table 6-1, the examination and observation are carried out for the period from before surgery day 120 to 180 after surgery of second eye. At Visit 0 and Visit 4A, the examination and observation of both eyes are carried out on the same day.

Both the examination and the observation may be per Visited on the same day if the day is within the window for the examination and observation of the eye concerned (first or second operated eye). Also examination and observation can be performed separately over days if these are performed within the set window.

Table 6-1 Eye Examinations Schedule

PROCEDURES/ MEASUREMENTS/ STATUS	Visit 0 (Preop)	Visit 00 (Op)	Visit 00A (Op)	Visit 1 (d1-2)	Visit 1A (d1-2)	Visit 2 (d7-14)	Visit 2A (d7-14)	Visit 3 (d30-60)	Visit 3A (d30-60)	Visit 4A (d120-180)
Informed Consent*	X									
Demographics	X									
Inclusion/Exclusion Criteria	X	1 st	2 nd							
Urine Pregnancy Test (female only)	X									
Intraocular Pressure	B			1 st	2 nd	1 st	2 nd	1 st	2 nd	B
Laser Flare Meter (mydriatic)						1 st	2 nd			(1 st ) (2 nd )
Slit Lamp Examination	B			1 st	2 nd	1 st	2 nd	1 st	2 nd	B
Dilated Fundus Examination	B					1 st	2 nd			B
Fundus visualization						1 st	2 nd			B
IOL Observations				1 st	2 nd	1 st	2 nd	1 st	2 nd	B
Lens decentration and tilt				1 st	2 nd	1 st	2 nd	1 st	2 nd	B
Subjective Posterior Capsule Opacification / Posterior Capsulotomy					1 st	2 nd	1 st	2 nd	1 st	2 nd
Subjective Symptoms	X b								X b	X b
Operation Records**			1 st	2 nd						
Ocular Concomitant Medications	B	1 st	2 nd	1 st	2 nd	1 st	2 nd	1 st	2 nd	B
Secondary Surgical Interventions				1 st	2 nd	1 st	2 nd	1 st	2 nd	B
Device Deficiencies	↔									
Adverse Events	↔									

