1st: First eye, 2nd: Second eye, B: Both eyes (1st eye and 2nd eye), Xb: Binocular Testing, X: Conduct[REDACTED], (1st) (2nd): If there is any inflammation sign at Visit 2 or Visit 2A, perform examination again.

\*: Consent continuously participate of this clinical study is obtained between 1st and 2nd implant.

\*\*: Operative Eye, Problems During Surgery, Other Procedures at Surgery, Insertion Instrument, Incision Site, Final Incision Size, anterior capsulotomy size, and Lens Information

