### 3) Postoperative Examinations

Below examination and observation are carried out at Visit 1/1A, Visit 2/2A, Visit 3/3A and Visit 4A.

- Visual acuity

Visual acuity is tested under photopic [REDACTED] using the 100% contrast chart at each measurement distance as below. [REDACTED]  
[REDACTED]  
[REDACTED]

- **Subjective Symptoms (Visit 3A, Visit 4A: Binocular)**

To the following inquiries by the investigator, the subject will declare the following Subjective symptoms.

- Intraocular Pressure (Visit 1/1A, Visit 2/2A, Visit 3/3A: Monocular (1st or 2nd eye), Visit 4A: Both eyes)

Perform tonometry using a contact or a non-contact ocular tonometer.

- Laser Flare Meter (Visit 2/2A: Monocular (1st or 2nd eye), Visit 4A: Both eyes)

Perform examination using a laser flare meter at mydriatic condition. If there is any inflammation sign at Visit 2 or Visit 2A in laser flare meter and Slit lamp examination, perform examination again at Visit 4A.

- Slit Lamp Examination (non-mydriatic or mydriatic)

(Visit 1/1A, Visit 2/2A, Visit 3/3A: Monocular (1st or 2nd eye), Visit 4A: Both eyes)

Record the presence or absence of clinically significant ophthalmologic findings.

- Dilated Fundus Examination (Visit 2/2A: Monocular (1st or 2nd eye), Visit 4A: Both eyes)

Record the presence or absence of clinically significant ophthalmologic findings.

- Fundus visualization (Visit 2/2A: Monocular (1st or 2nd eye), Visit 4A: Both eyes)

Indicate whether the investigational lens has caused any loss in fundus visualization that would alter a surgeon's ability to administer retinal treatment, as compared to experience with monofocal IOLs.

- IOL observation (Visit 1/1A, Visit 2/2A, Visit 3/3A: Monocular (1st or 2nd eye), Visit 4A: Both eyes)

[figure not shown]
Observe the IOL surface and the inside of the haptic and optic of the investigational lens with a slit-lamp microscope, and record the presence/absence of visible abnormal findings (debris on IOL surface, forceps mark on IOL surface, glistening, formation of membrane on IOL, pigmentation on IOL, etc.). And regarding the observed findings, evaluate the clinical significance. If the problem may negatively affect postoperative visual acuity, etc., handle it as the clinical significant, and if possible, take photos.

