## (3) Report of adverse events and evaluation of the causal relationship

All adverse events (related and unrelated to the medical device or test procedures) will be entered in the Adverse Event form. Surgically-related post-operative conditions that are normal consequences of the ocular surgery (see Appendix B) and not clinically relevant will be only reported as adverse events at the discretion of the investigator.

In addition, the investigator must document all serious adverse events (related and unrelated) on the Serious Adverse Event Form. Any device deficiencies will be entered in the device deficiency form within 24 hours

[figure not shown]
after confirming the event.

Adverse events will also be reported for any clinically relevant change from screening in any protocol specific safety parameter evaluated during the study, based upon an assessment by the investigator following exposure to an investigational product.

Regarding the relationship with the investigational lens, a judgment will be made whether “not related” or “related.” Adverse events will be reported for any change in an ongoing medication and/or addition of a new medication, based upon an assessment by the investigator.

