## APPENDIX B: Definition of Adverse Events

Following findings are not regarded as AE because that it is a series of wound healing reaction related to cataract surgery. However, when investigator judged it is not wound healing reaction, it is treated as AE.

- Edema or haze around sclerocorneal incision: Occurred by 1 month post surgery
- Fold or swelling of Descemet's membrane at central cornea: Occurred by 1 month post surgery
- Post surgery inflammation: Occurred by 3 months post surgery
- Raised IOP related to post operation inflammation and fibrin reaction: Occurred by 1 month post surgery

Investigator (or sub-investigator) should judge when the events below occurred after the test IOL implantation whether the events is AE or not.

If the events are regarded as AE, investigator must fill out AE forms in the electric case report forms.

- IOP: 10mmHg or more than 10 mmHg change from Visit 0 after 1 month post surgery
- Slit lamp findings (anterior and posterior segment): Worse than Visit 0  
(Ocular finding which is caused by inflammation related to cataract surgery is excluded.)
- Best corrected distance visual acuity: Worse than Visit 0 at the last exam (Visit 4A)

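### Does the plan need changing because laser flare has no reading before surgery, so its change from baseline cannot be computed?

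*Protocol*

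**What the plan says.** Protocol 9.6 sets one rule for all continuous safety variables: "descriptive statistics (mean, standard deviation, N, median, min and max) will be provided for actual value and change from baseline at each visit". Laser flare is in the list that follows. SAP 5.3 takes baseline as the last reading before exposure to the lens and names no other baseline for flare.

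In Protocol Table 6-1 the row "Laser Flare Meter (mydriatic" is blank at Visit 0. It has the operated eye at Visit 2 or 2A and a bracketed entry at Visit 4A. The footnote explains the brackets: "If there is any inflammation sign at Visit 2 or Visit 2A, perform examination again". The procedure text in Protocol 6(5)3) carries the heading "Laser Flare Meter (Visit 2/2A: Monocular (1 st or 2 nd eye), Visit 4A: Both eyes", and beneath it the qualifier "If there is any inflammation sign at Visit 2 or Visit 2A in laser flare meter and Slit lamp examination, perform examination again", which governs the Visit 4A reading.

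SAP 5.3.13 plans descriptive statistics for the flare value at the visits where it is collected, by first and second eye, plus a listing by subject, visit and eye. It does not mention change from baseline. SAP 5.3.5 does plan change from baseline for intraocular pressure.

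Protocol 10(3) adds a general reporting rule: "Adverse events will also be reported for any clinically relevant change from screening in any protocol specific safety parameter evaluated during the study", on the investigator's assessment.

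**The concern.** Taken literally, Protocol 9.6 promises a table that the schedule cannot supply. Protocol 10(3) speaks of change from screening, and flare has no screening value either. The study has a single arm, so a within-eye comparison would be the natural reference for a continuous safety measure.

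The one later flare reading is confined to eyes with an earlier sign of inflammation. A reader could set the Visit 4A mean beside the all-eye Visit 2/2A mean and draw a false trend. SAP 5.3.13 does not label Visit 4A as a selected subset. Unlike SAP 5.3.4 to 5.3.7, it also has no listing of eyes with missing follow-up, so an eye that was due and missed could be confused with one that was not due.

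Appendix B treats "Post surgery inflammation: Occurred by 3 months post surgery" as part of wound healing unless the investigator judges otherwise, so the adverse event tables need not fill the gap. At stake would be whether the study can say that flare rose, fell or settled.

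**Working it through.** **1. Schedule, from Protocol Table 6-1.**

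| Variable | Visit 0 | 1/1A | 2/2A | 3/3A | 4A |
|---|---|---|---|---|---|
| Intraocular pressure | both eyes | operated eye | operated eye | operated eye | both eyes |
| Slit lamp | both eyes | operated eye | operated eye | operated eye | both eyes |
| Laser flare | none | none | operated eye | none | only after a sign at 2/2A |

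Pressure is read in all eyes at 5 of 5 time points, flare at 1 of 5. The Visit 0 procedure list in Protocol 6(5)1) has no visible flare item either. Redaction is an unlikely explanation, because the flare row is visible and its Visit 0 cell is empty.

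**2. Eyes with a computable change.** Planned size is 60 subjects, 120 eyes. Eyes with a flare reading before exposure: 0. Change from baseline therefore has N = 0 of 120 at every visit.

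**3. What the analysis will produce.** Of the visible variables in Protocol 9.6, the SAP treats two as continuous. Pressure has a baseline and gets a change table (SAP 5.3.5). Flare has none and gets observed values only (SAP 5.3.13). Each matches the data collected.

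**4. The plan's own precision figure.** Half-width in SD units = t(0.975, n−1)/√n. At n = 60 this is 0.258, which agrees with the stated 0.26. It is a general figure for any mean in 60 eyes and says nothing particular about flare.

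**5. Size of the Visit 4A row.** The documents give no rate of inflammation signs. If 10% to 20% of 60 first eyes had one (an assumption):
- 0.10 × 60 = 6 eyes, half-width 1.05 SD
- 0.20 × 60 = 12 eyes, half-width 0.64 SD

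SAP 5.3.13 prints N and plans no interval for flare. A Visit 4A row with N of 6 or 12 under a Visit 2/2A row with N near 60 shows on its face that it is a subset.

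**6. Tracing missed re-readings.** The flare listing shows which eyes have a Visit 4A value. SAP 5.3.6 lists all slit lamp data from all visits for any eye with a postoperative abnormality. Setting the two side by side shows which eyes had a slit lamp sign and no repeat flare value. A sign seen only on the flare meter is harder to trace, because no threshold is visible.

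**7. The adverse event rule.** Fundus visualization, IOL observations, decentration and tilt, and capsule opacification also have no Visit 0 value, so the wording of Protocol 10(3) is general and not a flare requirement. Appendix B names the comparisons with Visit 0 that prompt a judgement: intraocular pressure, slit lamp findings and best corrected distance acuity. Flare is not among them.

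**8. Cost of collecting the values.** Up to 120 readings at Visit 0 plus up to 120 at Visit 4A gives 240. The "Dilated Fundus Examination" is scheduled for both eyes at both visits, but Protocol 6(4) lets examinations fall on different days and 6(5)1) accepts routine tests done before consent. A flare reading could therefore need a separate dilation.

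**The case for a change.** The strongest case for acting is that Protocol 9.6 and the schedule do conflict, and the SAP departs from 9.6 without saying so. Someone holding the report to the protocol will look for a flare change table and find none. A few words would prevent that: exempt flare in 9.6, call the Visit 4A row conditional in SAP 5.3.13, and count the eyes due and re-read.

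The conflict stands. So does the point that the Visit 4A eyes are selected and their mean should not be compared with the Visit 2/2A mean. The trigger wording is also loose. The footnote asks for any sign, while the procedure text names the flare meter and the slit lamp and leaves open whether both must show it. Neither says whether a sign in one eye brings in the fellow eye.

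The rest does not carry the case. The both-eyes heading cannot be read as a second reading in every eye, because the sentence beneath it makes the repeat conditional; the same Visit 4A label is used for other examinations since both eyes are seen that day. The missing follow-up listing is not a singular omission, as SAP 5.3.8 to 5.3.11 have none either. No document states an aim of measuring flare change from before surgery.

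**Conclusion.** The observation is correct, and no change follows. Flare change from baseline is unavailable in 0 + 120 = 120 of 120 eyes, and the SAP already plans accordingly by reporting observed values. The mismatch is a general protocol sentence applied to a variable it does not fit, a gap that the SAP's authors filled sensibly.

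A pre-operative reading and an all-eye Visit 4A reading would be a design preference costing up to 240 readings. They would be of no use for eyes already operated on, and the SAP was signed about 8 months after the planned start. One reading in every eye, a recheck where a sign was seen, and slit lamp at every postoperative visit is a fair trade-off. Rewording would change no number, because the flare table already prints N and comes with a listing by eye.

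The size is confined to one descriptive safety variable; no hypothesis, success criterion or conclusion depends on it. This rests on three things: the visible flare row is complete, the flare table is produced as SAP 5.3.13 describes, and the report's author reads the Visit 4A row as the selected subset it is.

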## 9.7 Interim Analysis

No interim analysis is planned.

## 9.8 Sample Size Justification

The 60 eligible subjects will be bilaterally implanted with the AcrySof IQ PanOptix IOL (TFNT00). The purpose of this study is to describe safety and effectiveness of the investigational lens. The sample size is not determined on the basis of a statistical power calculation. With a sample size of 60, a two-sided 95% CI for the mean based on the t-statistic will extend 0.26\*SD units from the observed mean. Also, a 95% confidence interval of 50% (30/60) is (36.8%, 63.2%) based on the exact method.

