The remaining one lens is TFNT00 developed by US Alcon (hereinafter called the investigational lens). It was given the CE mark in June 2015 and is now commercially available in EU. As with the Alcon® AcrySof® IQ ReSTOR® Single Piece of Alcon Japan (medical device approval number: 22000BZX00970000; hereinafter called SN6AD1) approved in Japan, the investigational lens provides multiple focuses based on the diffractive structure of the optical zone. SN6AD1 is a bifocal intraocular lens designed to have a diffractive zone with 3.6 mm around the optical part center, with an add power of +3D and a near focal distance (theoretical value) of about 40 cm. The investigational lens is designed to have a diffractive zone with 4.5 mm around the optical part center. This design change of the diffractive zone allows focusing on distance, intermediate, and near objects. The investigational lens has an add power of +2.17D and +3.25D and intermediate and near focal distances (theoretical value) of about 60 and 40 cm, respectively. It has an intermediate focus of 60 cm in addition to the distance and near (40 cm) focuses of SN6AD1. A non-clinical study (simulation with Badal images) performed to compare the visions potentially

achieved with the investigational lens and SN6AD1 showed that the investigational lens had a potential to provide equivalent distance and near visions to SN6AD1 and better intermediate visions at 80 and 60 cm^9). In general, diffractive lenses are structurally associated with diffraction loss and resulting reduced contrast sensitivity because not all the lights passing through the lens are focused on the retina. [REDACTED]

[REDACTED]

[REDACTED] A clinical study of SN6AD1 (C-07-44) showed an uncorrected distance VA (logMAR) of  $0.03 \pm 0.14$ , uncorrected near vision of  $0.04 \pm 0.12$ , and normal photopic contrast sensitivity for both distance and near visions at 1 year postoperation. Although these visual acuity values from Badal images were obtained from a simulation, the investigational lens can correct not only distance and near visions, but also an intermediate vision of about 60 cm and is therefore expected to contribute to the improved quality of vision after cataract surgery.

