## 9.4 Effectiveness Analysis

The objective of this study is to describe safety and effectiveness of the investigational lens (TFNT00) when implanted to replace the natural lens following cataract removal. Monocular analysis will be performed at both first and second eyes. Binocular analysis will be performed for binocular testing parameters.

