#### 9.4.1.2 Analysis Method

Decimal monocular photopic best corrected distance visual acuity (5 m) and decimal monocular photopic distance corrected intermediate visual acuity (60 cm) will be categorized as follows.

[figure not shown]
- $< 0.5$
- $0.5 - < 0.7$
- $0.7 - < 1.0$
- $1.0 -$

[figure not shown]
Decimal monocular photopic distance corrected near visual acuity (40 cm) will be categorized as follows.

- $< 0.4$
- $0.4 -$

The N and percent of each category will be provided by visit. For these decimal visual acuity, descriptive statistics (geometric mean, dispersion factor (DF), N, median, min and max) will be provided by visit. Descriptive statistics (arithmetic mean, standard deviation, N, median, min and

max) will also be provided for logMAR visual acuity by visit.

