4.3 Statistical Methods for Efficacy Analyses

Distance visual acuity (5 m), intermediate visual acuity (60 cm) and intermediate visual acuity (80 cm) will be categorized as follows.

- < 0.5
- $0.5 - < 0.7$
- $0.7 - < 1.0$
- $1.0 \leq$

Near visual acuity (40 cm) will be categorized as follows.

- < 0.4
- $0.4 \leq$

The N and percent of each category will be provided by visit. For these decimal visual acuity, descriptive statistics (geometric mean, dispersion factor (DF), N, median, min and max) will be provided by visit. Descriptive statistics (arithmetic mean, standard deviation, N, median, min and max) will also be provided for logMAR visual acuity by visit.

In order to compute the mean of decimal visual acuity correctly, the geometric mean must be used. The formulas for transforming from decimal acuity to logMAR score and back are as follows.

$$\text{LogMAR} = -\text{Log}_{10} (\text{Decimal Acuity})$$

$$\text{Decimal Acuity} = \text{antiLog} (-\text{LogMAR}) = 10^{-\text{LogMAR}}$$

The mean of decimal acuity is defined as

[figure not shown]
$$\text{Mean of Decimal Acuity} = 10^{\text{mean of} (-\text{Log MAR})} = 10^{\text{mean of} \text{ Log}_{10} (\text{Decimal Acuity})}$$

[figure not shown]
For geometric means, dispersion factors (DF) corresponds to standard deviations and defined as:

$$+DF = 10^{(\text{mean of } \log_{10}(\text{Decimal Acuity}) + \log(\text{SD}))} - 10^{\text{mean of } \log_{10}(\text{Decimal Acuity})}$$

$$-DF = 10^{(\text{mean of } \log_{10}(\text{Decimal Acuity}))} - 10^{(\text{mean of } \log_{10}(\text{Decimal Acuity}) - \log(\text{SD}))}$$

where, Log (SD) is a standard deviation of \log_{10} (Decimal Acuity).

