5.4 Interim Analysis for Safety

No interim analysis is planned for this study.

6 Pharmacokinetic Analysis Strategy

Not Applicable.

7 Analysis Strategy for Other Endpoints

[figure not shown]
Not Applicable

8 Sample Size and Power Calculations

The 60 eligible subjects will be bilaterally implanted with the AcrySof IQ PanOptix IOL (TFNT00). The purpose of this study is to describe safety and effectiveness of the investigational lens. The sample size is not determined on the basis of a statistical power calculation. With a sample size of 60, a two-sided 95% CI for the mean based on the t-statistic will extend $0.26 * SD$ units from the observed mean. Also, a 95% confidence interval of 50% (30/60) is (36.8%, 63.2%) based on the exact method.

9 References

No references.

Date/Time (mm/dd/yyyy GMT):	Signed by:	Justification:
11/29/2017 08:12:36	[REDACTED] [REDACTED]	[REDACTED]
11/29/2017 20:42:53	[REDACTED] [REDACTED]	[REDACTED]
12/01/2017 14:48:53	[REDACTED] [REDACTED]	[REDACTED]

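### Should the plan commit to reporting the confidence intervals it uses to justify 60 subjects?

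*Protocol*

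**What the plan says.** On sample size, Protocol 9.8 and SAP 8 carry the same text. The size is not based on power. The Protocol goes on: "With a sample size of 60, a two-sided 95% CI for the mean based on the t-statistic will extend" 0.26 SD from the observed mean. SAP 8 repeats this and the second figure: "Also, a 95% confidence interval of 50% (30/60) is (36.8%, 63.2%) based on the exact method".

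On outputs, Protocol 9.4.1.2 says of the acuity categories: "The N and percent of each category will be provided by visit". Decimal acuity gets a geometric mean, dispersion factor (DF), N, median, minimum and maximum. For the log scale, SAP 4.3 says: "Descriptive statistics (arithmetic mean, standard deviation, N, median, min and max) will also be provided for logMAR visual acuity by visit". It introduces the DF as follows: "For geometric means, dispersion factors (DF) corresponds to standard deviations and defined as", and then gives the formulas. The general summary rule in SAP 3 and the subgroup text in SAP 4.5 list the same kinds of statistics. No interval or standard error appears in any of these places.

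On purpose, Protocol 9.4.1.1 and SAP 4.2 plan no hypothesis test. SAP 1.1 calls all analysis descriptive, and the SAP's executive summary defines no success criterion. On the unit of analysis, Protocol 9.4 says: "Monocular analysis will be performed at both first and second eyes".

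**The concern.** With no comparator, test or success criterion, effectiveness is purely a matter of estimation, and an interval is the usual way to say how well a quantity is estimated. The sponsor uses intervals to defend the number 60, yet the visible output lists do not include them. The dispersion measure printed with each geometric mean is the DF, which describes spread between eyes. A reader who took it for the precision of the mean would think the estimate much less certain than it is. The category percentages have no uncertainty measure listed. If the intervals could not be recovered, or if a conclusion depended on them, the primary results would be incomplete.

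**Working it through.** **1. Reproduce the plan's figures.** Inputs: n = 60 and 95% two-sided, both from Protocol 9.8.

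- Mean: half-width = t(0.975, 59)/√60 = 0.2583 SD, stated as 0.26.
- Proportion: the exact (Clopper-Pearson) interval for 30/60 is 36.81% to 63.19%, stated as 36.8% to 63.2%.
- With n = 120 the results would be 0.181 SD and 40.7% to 59.3%. The stated figures therefore belong to one eye per subject, which fits analysis of first and second eyes separately.

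Both figures are right for the methods named.

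**2. Can each interval be recovered from the planned outputs?**

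| Interval | What is needed | Planned? |
|---|---|---|
| Mean logMAR, t-based | mean, SD, N | Yes (SAP 4.3) |
| Geometric mean of decimal acuity | back-transform of the row above | Yes |
| Category percentage, exact | count and N | Yes (N and percent) |

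**3. Worked illustration.** The only acuity SDs in the documents are in Protocol 1(1): "A clinical study of SN6AD1 (C-07-44) showed an uncorrected distance VA (logMAR) of" 0.03 with SD 0.14, and uncorrected near 0.04 with SD 0.12. They come from a different, bifocal lens and from uncorrected acuity at 1 year, whereas the primary variables here are best corrected or distance corrected. They are used as assumptions only.

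- Distance: 0.2583 × 0.14 = 0.0362 logMAR. The interval is 0.03 ± 0.0362, or −0.006 to 0.066.
- Back-transformed: geometric mean 10^(−0.03) = 0.933, interval 10^(−0.066) to 10^(0.006) = 0.859 to 1.014.
- Near: 0.2583 × 0.12 = 0.0310 logMAR.
- Percentages for assumed counts: 54/60 gives 79.5% to 96.2%; 57/60 gives 86.1% to 99.0%; 60/60 has a lower bound of 94.0%.

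**4. The DF beside the interval.** Same assumed values.

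- +DF = 10^(−0.03+0.14) − 10^(−0.03) = 1.288 − 0.933 = 0.355.
- −DF = 10^(−0.03) − 10^(−0.03−0.14) = 0.933 − 0.676 = 0.257.
- Mean minus DF to mean plus DF is therefore 0.676 to 1.288, against a confidence interval of 0.859 to 1.014.
- On the log scale, one SD is 1/0.2583 = 3.87 half-widths. That ratio depends only on n = 60 and holds for any variable summarised by mean and SD, so it does not measure a fault in this plan.
- The SD can be read back from the DF: log10(1 + 0.355/0.933) = 0.14.

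**5. Fewer than 60 eyes.** No missing data are imputed (Protocol 9.5). With 54 eyes (assumed) the half-width is 0.273 SD, still close to the stated 0.26.

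**The case for a change.** The strongest case for a change is that a study whose purpose is estimation should fix in advance how it will express uncertainty. Being able to derive an interval is not the same as planning one. Prespecification would settle the method and the unit of analysis, and would close off the error of pooling 120 correlated eyes as if independent, which would shrink the half-width from 0.258 SD to 0.181 SD. The cost would be a few lines and some table columns.

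Part of this stands. Intervals are good practice, the visible lists do not name them, and adding them would be cheap. The rest is weaker. Protocol 9.4 already provides for monocular analysis of first and second eyes, and the sample size sections already name the t-based and exact methods at n = 60, so an analyst who wants an interval has both method and unit. Confusing the DF with precision is speculative: SAP 4.3 equates it with a standard deviation and gives its formula, and N, median, minimum and maximum are listed with it. A sentence saying what precision 60 subjects would give is also complete without a promise to print intervals, so the documents do not contradict themselves.

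**Conclusion.** The observation is accurate for the visible text: interval widths are the only quantitative support for 60 subjects, and no visible primary output list names an interval. It does not call for a change. The widths are correct, the study has no decision rule that an interval would feed, and the planned statistics determine every interval. Following the plan as written gives sound descriptive results, and adding the columns would alter no estimate or conclusion. Whether to print them is a matter of presentation that the sponsor can settle when the tables are laid out.

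This rests on the mean, SD, N and percent being reported by visit as planned, and on first and second eyes being kept separate. The logMAR and percentage examples are illustrations based on assumed SDs and counts. The SAP contents page places section 4.3 on pages 9 to 13, and the list of tables has three blank entries on page 12, so much of that section appears to be redacted. Whether an interval is specified there cannot be checked, but the conclusion does not depend on it.
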